#### 4.1.6 Treatment Compliance

At each study visit, the participant will be instructed to bring their pill bottles with them and the number of remaining pills will be counted and recorded. Treatment compliance will be defined as actual number of pills taken divided by the expected number of pills  $\times$  100. In order to allow for subjects who discontinue IP early in the compliance calculation, the number of expected dosing occasions will be calculated as the number of scheduled dosing occasions up to and including the last available dosing occasion for that subject.

Mean treatment compliance will be listed and summarized for the Safety set, as well as the number and percent of those taking greater than or equal to 85% of the assigned study drug doses. A participant’s dosing compliance will be calculated as the percentage of visits for which dosing compliance was met.

## 4.2 EFFICACY ANALYSES

### 4.2.1 Summary of efficacy analyses

Efficacy analysis will be performed at the end of the 12-week study during Final Analysis.

**Table 4-3 Summary of estimands for efficacy analyses**

Endpoint (mITT)	Population Level Summary (Analysis)	Section
Change from baseline to Week 12:		
MDS-UPDRS Sum of Part II+III	Mean difference between treatment groups (MMRM)	4.2.3
PDQ-39	Mean difference between treatment groups (MMRM)	4.2.3
PGI-S	proportion of participant s who improved from baseline (GLIMMIX)	4.2.3
CGI-S	proportion of participant s who improved from baseline (GLIMMIX)	4.2.3
MDS-UPDRS Part II	Mean difference between treatment groups (MMRM)	
MDS-UPDRS Part III	Mean difference between treatment groups (MMRM)	4.2.3
MDS-UPDRS Part I	Mean difference between treatment groups (MMRM)	4.2.3
NMSS	Mean difference between treatment groups (MMRM)	4.2.3
CSBM	Mean difference between treatment groups (MMRM)	4.2.3
ESS	Mean difference between treatment groups (MMRM)	4.2.3
Schwab and England ADL Scale	Mean difference between treatment groups (MMRM)	4.2.3
PAGI-SYM	Mean difference between treatment groups (MMRM)	4.2.3
PAC-QoL	Mean difference between treatment groups (MMRM)	4.2.3
PAGI-QoL	Mean difference between treatment groups (MMRM)	4.2.3

## 4.2.2 Primary Analysis

### 4.2.2.1 Primary Analysis

There is no primary efficacy endpoint. The primary tolerability endpoint is the proportion of participants in the Safety Set who discontinue treatment up to Week 12 and will be reported with the Safety Analysis.

The other primary safety analyses are described in [Section 4.3.2](#).

## 4.2.3 Secondary Efficacy Analyses

The efficacy endpoints (as changes from baseline at Week 12) will be evaluated in hierarchical order as described in [Section 2.4](#). The following endpoints will be evaluated:

- Movement Disorder Society-sponsored revision of the Unified Parkinson's Disease Rating Scale (MDS-UPDRS) Parts II + III
- Parkinson's Disease Questionnaire (PDQ-39) summary index
- Patient Global Impression-Severity (PGI-S)
- Clinician Global Impression of Severity (CGI-S)
- MDS-UPDRS Part II
- MDS-UPDRS Part III
- MDS-UPDRS Part I
- Non-Motor Symptom Scale (NMSS) total score
- Complete Spontaneous Bowel Movement Score (CSBM)
- Epworth Sleepiness Scale (ESS) total score
- Schwab and England Activities of Daily Living (SE-ADL) Scale
- Patient Assessment of Upper Gastrointestinal Disorders Severity Index (PAGI-SYM)
- Patient Assessment of Constipation Quality of Life (PAC-QoL)
- Patient Assessment of Gastrointestinal Disorders Severity Quality of Life (PAGI-QoL)

The estimand for the key efficacy endpoint is defined as follows:

- A. Population: Participants with Parkinson's Disease as defined by inclusion/exclusion criteria and in the modified Intent-to-Treat (mITT) population.
- B. Variable: Change from baseline to Week 12 in the MDS-UPDRS Parts II + III score.
- C. Intercurrent Events:
  - a. Premature Discontinuation of Study Treatment
  - b. Initiation of PD Medication for Treatment of Motor Features
- D. Summary: Treatment differences of the least-squared mean (LSM) change from baseline at Week 12 in the MDS-UPDRS Parts II + III summary index between 50, 100, or 200 mg IKT-148009 vs placebo.

For data that are missing due to premature discontinuation of study treatment or initiation of PD medication, no specific imputation will be done. If possible, the collection of data will be continued and used according to the treatment policy strategy. Descriptive statistics for each endpoint will be presented as change from baseline by treatment group and visit.

The differences between the dose levels versus placebo at Week 12 in the continuous secondary endpoints will be estimated using a Mixed Model for Repeated Measures (MMRM) using the mITT Set.

For each endpoint and treatment group, the null hypothesis will be  $H_0: \delta = 0$  and the alternative hypothesis will be  $H_0: \delta \neq 0$ , where  $\delta$  = treatment difference =  $(\bar{x} - \mu)$ .

For participants  $i=1, \dots, I$  and repeated observations  $j=1, \dots, J$ , the MMRM model can be parameterized as

$$\mathbf{Y}_i = \mathbf{X}_i \boldsymbol{\beta} + \mathbf{Z}_i \mathbf{b}_i + \boldsymbol{\epsilon}_i$$

Where  $\mathbf{Y}_i$  = a  $J_i$  dimensional vector of outcome measurements for the  $i^{\text{th}}$  participant,

$\boldsymbol{\beta}$  = a  $p$  dimensional vector containing the fixed effects (baseline, treatment effect, time),

$\mathbf{X}_i, \mathbf{Z}_i = (J_i \times p)$  and  $(J_i \times q)$  dimensional design matrices of known covariates,

$\mathbf{b}_i = q$  dimensional vector containing the random effects ( $\mathbf{b}_i \sim N(0, D)$ ) and

$\boldsymbol{\epsilon}_i = J_i$  dimensional vector of residual components ( $\boldsymbol{\epsilon}_i \sim N(0, \Sigma_i)$ ).

The MMRM will include the observed change from baseline from Week 4, Week 8, and Week 12 as the response values, baseline value as a covariate, and treatment group, visit, and treatment group  $\times$  visit interaction term as fixed factors. An unstructured covariance structure will be assumed first. If this model does not converge, Heterogeneous Autoregressive (1) (ARH[1]), Heterogeneous Compound Symmetry (CSH), Autoregressive (1) (AR[1]) or Compound Symmetry (CS) covariance structure will be used (in this order). The denominator degrees of freedom will be computed using the Kenward-Roger method.

The least square (LS) means estimate for each treatment group, SEM, and LS mean difference between different dose levels and placebo will be provided, along with the 95% confidence intervals (CI) and  $p$ -value, for each assessment. Only the LS means for Week 12 will be used for statistical comparison.

Categorical endpoints (PGI-S, CGI-S) will be analyzed using the GLIMMIX procedure for binomial data with the logit link. The model will include the observed binomial values from all post-baseline visits as the response values and the treatment group, visit and the interaction between the treatment group and visit as fixed factors. The baseline value will be used as a covariate in the model. “Improved” is defined as at least a whole number decrease in score for PGI-S and CGI-S. Response values will be the proportion who improved since baseline at each post-baseline visit. The proportion who improved at each assessment will be presented, along with the odds ratio, 95% CI and  $p$ -value. Only the proportion who improved at Week 12 will be used for statistical comparison.

Endpoints will be tested in the order presented in [Section 2.4](#) with 2-sided  $\alpha=0.05$ . Endpoints not compared as part of the hierarchical testing procedure will be reported for descriptive purposes only.

Each of the secondary efficacy endpoints is described in [Section 3.2](#).

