1.3 Schedule of Activities (SoA)

Procedures	Screening Visit	Baseline	Treatment Period (12 Weeks \pm 2 days)				Safety Follow-up
			2	3	4	EOS/EW	
Study Visit	SW	1					
Week	Day -28 to -1	Day 1	2	4	6	8	14 \pm 2 days
Written informed consent	X						
Enrollment Authorization Form	X						
Outpatient visits ^m	X	X	X	X	X	X	X
Demographics ^a	X						
Vital signs ^b	X	X	X	X	X	X	X
Height and weight ^c	X	X	X	X	X	X	X
12-Lead ECG (triplicate) ^d	X	X	X	X	X	X	X
Review concomitant medications	X	X	X	X	X	X	X
Medical history	X						
Complete physical examination	X						
Modified Hoehn and Yahr ^e	X						
Montreal Cognitive Assessment	X						
Telephone contact ^f	X ^k	X	X	X	X	X	
C-SSRS	X	X	X	X	X	X	X
Safety laboratory tests	X	X	X	X	X	X	X
Pharmacokinetics (Blood)	X		X	X	X	X	
Pregnancy test ^g	X	X					X
MDS-UPDRS Parts I, II, and III	X	X	X	X	X	X	X

Confidential

IkT-148009-201

V 6.4

Procedures	Screening Visit	Baseline		Treatment Period (12 Weeks ± 2 days)				Safety Follow-up
		SV	1	2	4	6	8	
Week	Day -28 to -1	Day 1	2	4	6	8	10	4 EOS/EW
Epworth Sleepiness Scale (ESS)	X							X
PAGI-SYM, PAC-QoL, PAGI-QoL	X		X		X			X
NMSS	X		X		X			X
SE-ADL	X		X		X			X
PDQ-39	X		X		X			X
CGI-S	X		X		X			X
PGI-S	X		X		X			X
CSBM	X ^k		X ^k		X ^k			X ^k
Dispense/collect (unused) investigational product	X ^h		X		X			X ⁱ
Review dosing compliance	X	X	X	X	X	X		X
AEs/serious AEs	X	X	X	X	X	X		X
Skin biopsy ⁿ	X		X		X			X
CSF Collection ⁿ	X							X
Ophthalmic exams ^l	X							X

AE=adverse event; BP=blood pressure; CGI-C=clinical global Impression of change; CSBM=Complete Spontaneous Bowel Movement Score; CSF=cerebrospinal fluid; C-SRS=Colombia suicide severity rating scale; ECG=electrocardiogram; EOS=end of study; EW=early withdrawal; HR=heart rate; MDS-UPDRS=Movement Disorder Society-sponsored revision of the Unified Parkinson's Disease Rating Scale; NMSS=Non-Motor Symptom Scale; QoL=quality of life; PAC-QoL=Patient Assessment of Constipation Quality of Life; PAGI-QoL=Patient Assessment of GI Disorders Severity Questionnaire; PAGI-SYM=Patient Assessment of Upper GI Disorders Severity Index; PDQ=Parkinson's Disease Questionnaire; PGI-S=Patient Global Impression-Severity; RR=respiratory rate; SE-ADL=Schwab and Englund Activities of Daily Living Scale.

- a. Demographics include age, race, ethnicity, and sex.
- b. Vital Signs (Temperature, BP, HR, and RR) including orthostatic blood pressure measurements. At Baseline only, vital signs must be measured 3 times over the course of an hour.

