4.1. Overall Design

This is a 12-Week, randomized, double-blind, multi-center, placebo-controlled dose-ranging clinical trial of three Ikt-148009 doses in patients with untreated PD designed to assess safety, tolerability, and exploratory efficacy. It will enroll approximately 120 participants at up to

40 sites across the United States (US) using two randomization schemas. First, participants will be randomized across the 50 mg, 100 mg or placebo groups. Once 5 people have been randomized to each of the 50 mg, 100 mg or placebo groups, additional participants will be randomized as detailed in Section 7.3 to the 50 mg, 100 mg, 200 mg or placebo groups.

After signing the informed consent form (ICF), participants will undergo screening to evaluate their eligibility. The screening period will last up to 28 days before enrollment and randomization. An Enrollment Authorization Committee (EAC) will be responsible for reviewing screening data and confirming the eligibility and suitability of participants. This process will be outlined in the EAC charter. Those selected will be enrolled and randomized to one of two active IkT-148009 arms (50/100 mg) or a placebo arm (1:1:1) using interactive voice/web response system (IVRS/IWRS) during the first part of the study, then randomized to one of three active IkT-148009 arms or a placebo arm according to the table in section 7.3 once the 200mg dose is implemented. All clinical staff, study investigators, and participants will be blinded to study assignments throughout the trial.

Enrolled participants will have eaten within 2 hours prior to reporting to the site on Day 1 (Baseline) and undergo protocol-mandated procedures. Meals should not include citrus fruits or juice and they should not be consumed within 6 hours on either side of dosing. Each participant will self-administer the study intervention on-site at the first treatment visit and then at home, as per treatment assignment. At home, enrolled participants should eat a meal within one hour prior to dosing. The treatment period consists of outpatient visits at Weeks 1, 4, 8, and 12. A safety follow-up will occur at Week 14.

Telephone contacts at Weeks 2, 6, and 10 will occur to review and document changes in concomitant medications, assess dosing compliance, tolerability, and document/address any adverse events.

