9.2.8. Suicidal Ideation and Behavior Risk Monitoring

Patients with PD may occasionally develop suicidal ideation or behavior.

Participants being treated with IkT-148009 should be monitored appropriately and observed closely for suicidal ideation and behavior (SIB) or any other unusual changes in behavior throughout the study. Participants who experience signs of SIB should undergo a risk assessment.

All factors contributing to SIB should be evaluated and consideration should be given to discontinuation of the study intervention.

During the informed consent process, families and caregivers of participants being treated with IkT-148009 should be alerted about the need to monitor participants for the emergence of SIB and to report such symptoms immediately to the study investigator.

Baseline assessment of SIB/intervention-emergent SIB will be monitored throughout the study period using the C-SSRS. The C-SSRS will be assessed by trained personnel only. The scale consists of 4 categories: suicidal ideation, intensity of suicidal ideation, suicidal behavior, and actual/potential lethality which can be answered by Yes or No. At the screening visit the questionnaire for the past 6 months will be used, and for all other visits the version “Since the last visit” will be administered.

At each suicidality assessment, participants thought to have significant suicidal ideation with actual plan and intent or suicidal behavior must be evaluated by a clinician or mental health professional skilled in the evaluation of suicidality, who will determine if it is safe for the participant to continue in the trial. Specific criteria that indicate a need for further assessment include:

- Suicidal ideation associated with actual intent and/or plan in the past 6 months; (a “YES” answer to C-SSRS questions 4 “some intent to act without specific plan” or 5 “specific plan and intent”).
- Previous history of suicide behaviors in the past 5 years (a “YES” answer to any of the suicidal behavior items of the C-SSRS with the behavior occurring in the past 5 years).
- The investigator’s judgment that a risk assessment is warranted.

Participants who respond “Yes” to items 4 or 5, or to any behavioral question of the C-SSRS on more than one occasion during the trial may be discontinued from the trial.

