### 1.3.3 Sample Size and Statistical Power Considerations

A group size of 30 participants per dose was deemed sufficient to evaluate the potential safety and tolerability of IKT-148009. A sample size of 30 per group would provide > 80% power to detect a 5 point difference in the change from baseline UPDRS II + III between groups with a standard deviation of 6 points, a drop-out rate of 10%, and alpha = 0.05. Secondary measures will use appropriate descriptive statistics to assess study outcomes.

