## 2.3 DEFINITIONS AND CONVENTIONS FOR DATA HANDLING

### 2.3.1 Baseline Definition

Unless otherwise noted, the last value observed prior to the first administration of study intervention on Day 1 will be the baseline value. If there is no value prior to the study intervention, then the baseline value will not be imputed, and will be set to missing.

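### The MMRM for MDS-UPDRS adjusts for the Day 1 score alone, with one slope for all visits; a screening score, if confirmed as collected, could be added for a gain in precision at no data cost

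*SAP*

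**What the plan says.** SAP 4.2.3 lists the terms of the MMRM as "baseline value as a covariate, and treatment group, visit" and the treatment-by-visit interaction, fitted to change at Weeks 4, 8 and 12. It uses an unstructured covariance first and Kenward-Roger degrees of freedom. No covariate-by-visit term is listed. SAP 2.3.1 makes baseline a single measurement: "the last value observed prior to the first administration of study intervention on Day 1 will be the baseline value". Table 2-1 places it on Study Day 1.

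In the Protocol's Schedule of Activities (1.3), the row "MDS-UPDRS Parts I, II, and III" carries seven marks in the text copy. The outpatient-visit and C-SSRS rows carry the same number. Protocol 9.2.8 confirms that C-SSRS is done at screening: "At the screening visit the questionnaire for the past 6 months will be used". Protocol 4.1 gives the interval: "The screening period will last up to 28 days before enrollment and randomization".

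On power, SAP 1.3.3 states: "A sample size of 30 per group would provide > 80% power to detect a 5 point difference" in change in Parts II+III, "with a standard deviation of 6 points, a drop-out rate of 10%, and alpha = 0.05".

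**The concern.** A rater-scored scale varies from visit to visit for reasons unrelated to disease state. A second untreated score helps to separate a participant's underlying level from that noise, so it can lower the residual variance of the Week 12 contrast. It is fixed before randomisation, so adjusting for it leaves the estimand unchanged and does not bias the comparison.

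Separately, a single slope on the Day 1 score assumes that this score predicts change equally well at Weeks 4, 8 and 12. If its predictive value fades over time, the common slope is a compromise at the visit that matters. This second point does not depend on whether a screening score exists.

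Parts II+III at the high dose is the first test in SAP 2.4. If it fails, every later comparison is nominal, so precision on this endpoint is worth more than on any other.

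**Working it through.** **1. Is there a screening score?** Protocol 4.1 says: "The treatment period consists of outpatient visits at Weeks 1, 4, 8, and 12". If Week 1 is a separate visit, there are six in-person visits after screening (Day 1, Weeks 1, 4, 8, 12 and 14), and a seventh mark points to screening. But Week 1 may simply mean Day 1: Protocol 4.1 puts the ESS at Weeks 1 and 12, while SAP 3.2.10 puts it at Visit 1 (baseline) and Week 12. Then only five visits follow screening, and seven marks exceed even those five plus screening. The counts are also unreliable elsewhere: PGI-S shows four marks against five times in Protocol 4.1. The firmest evidence is that the row matches the outpatient-visit and C-SSRS rows, and C-SSRS is done at screening. A screening score is very likely, but not established.

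**2. The SAP's own power.** Inputs from SAP 1.3.3: difference 5, SD 6, 30 per group, 10% dropout (30 × 0.9 = 27), alpha 0.05, two-sided (SAP 4.2.3). The noncentral t gives 85.2% at 27 per group. The claim of more than 80% is reproduced.

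**3. Formula for the gain.** Assume equal variance at each visit. Let b be the Day 1–Week 12 correlation, s the screening–Week 12 correlation and q the screening–Day 1 correlation. With the Day 1 score alone, the residual variance is proportional to 1 − b². Adding the screening score removes the fraction

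(s − qb)² / [(1 − q²)(1 − b²)].

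**4. Range of the gain.** All correlations are assumptions.

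- Equal correlation r throughout: the variance ratio reduces to (1 + 2r)/(1 + r)². This is 0.889, 0.830, 0.802 and 0.776 at r = 0.5, 0.7, 0.8 and 0.9, a cut of 11%, 17%, 20% and 22%.
- b = 0.80 with screening and Day 1 more alike than either is to Week 12:

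| q | s | Variance cut |
|---|---|---|
| 0.85 | 0.78 | 0.10² / (0.2775 × 0.36) = 10.0% |
| 0.85 | 0.75 | 0.07² / (0.2775 × 0.36) = 4.9% |
| 0.90 | 0.78 | 0.06² / (0.19 × 0.36) = 5.3% |
| 0.90 | 0.75 | 0.03² / (0.19 × 0.36) = 1.3% |

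- Pure AR(1) decay without measurement error: s = qb, so the numerator and the gain are zero.

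**5. In power terms.** Take SD 6 as the SD of change and b = 0.8. Then 2σ²(1 − 0.8) = 36, so σ² = 90. With the Day 1 score alone the residual variance is 90 × 0.36 = 32.4 (SD 5.69), and power for 5 points at 27 per arm is 88.6%.

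- Equal correlation of 0.8: 32.4 × 0.802 = 26.0 (SD 5.10), power 94.2%.
- The four cases in the table: power 89.0% to 91.6%.
- AR(1): power stays at 88.6%.

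If SD 6 is instead already baseline-adjusted, the equal-correlation case at 0.8 runs from 85.2% to 91.8%. A simulation of four arms of 27 on that reading gave 85.2% and 92.0%.

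**6. The common slope.** Under equal correlation and equal variance, the slope of change on the Day 1 score is the same at every visit and nothing is lost. Under decaying correlation the slopes differ by visit. I have not put a figure on that loss.

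**The case against.** The strongest reply is that nothing is wrong. A baseline-adjusted MMRM with unstructured covariance is valid, and the stated power is met on the plan's inputs. The trial has no primary efficacy endpoint (SAP 1.2.2), and the Protocol calls efficacy exploratory. SAP 1.3.1 reports 126 participants enrolled after Protocol version 6.1, against about 120 planned, so the sample is not short. All of this stands, and it limits the point to an improvement.

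The reply also holds against three stronger readings that a reader might infer:

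- That a second pre-dose MDS-UPDRS certainly exists for every participant. No prose says so, the eligibility criteria do not use one, and the mark counts are unreliable.
- That power would rise to 94.2%. This needs the screening score, taken up to 28 days earlier, to predict Week 12 as well as the Day 1 score does, and screening and Day 1 to agree no better than Day 1 and Week 12. The documents support neither. ARH(1), the SAP's first fallback covariance, has the decaying form under which the gain is nil.
- That the planned analysis is underpowered or biased without the change. It is not.

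What the reply does not answer is why an informative pre-randomisation score, if collected, should go unused. The SAP gives no reason. With no MDS-UPDRS threshold for entry, selection on the screening score is not an evident obstacle.

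**Conclusion.** The point holds as an optional gain in precision, conditional for the screening covariate on confirming the SoA mark. The gain in residual variance is 0% to about 22%, depending on correlations that the documents do not give. About 1–10% applies when screening and Day 1 correlate 0.85–0.90, Day 1 and Week 12 correlate 0.80, and screening and Week 12 correlate 0.75–0.78. With SD 6 as the SD of change and a Day 1–Week 12 correlation of 0.8, power for 5 points lies between 88.6% (no gain) and 94.2% (equal correlation). The covariate-by-visit terms are worth adding in either case.

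**What to change.** Check the original SoA for an MDS-UPDRS mark at screening. Then, before unblinding, amend SAP 4.2.3 as follows:

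- Add the interaction of the Day 1 score with visit, whatever the SoA shows.
- If the screening assessment is confirmed, add the screening score of the same part or sum as a second covariate, with its own visit interaction, in the models for Parts II+III, II, III and I.
- Where the screening score is missing, set the covariate to the overall screening mean across all arms, so that nobody leaves the model. Do the same where the screening score was itself used as baseline because Day 1 was missing, which SAP 2.3.1 might allow; otherwise one measurement would enter twice.
- Keep change from the Day 1 value as the response, so the endpoint and estimand are unchanged.

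The cost is a short addition to the SAP and a few degrees of freedom. No new data are needed.

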#### 4.2.4 Other Efficacy Analyses

The exploratory endpoints are:

- Phosphorylated alpha-synuclein aggregates in skin and
- Phosphorylated alpha-synuclein aggregates in CSF

